10.2. Participant Withdrawal

10.2.1. Participant Withdrawal of Consent

A participant may withdraw consent for:

- Treatment
- Follow-up visits
- Non-patient contact follow-up, e.g., medical records checks

Withdrawal of consent for follow-up should be accompanied by documentation of the reason for withdrawal.

Participants requesting withdrawal should be informed that withdrawal of consent for follow-up may jeopardise the public health value of the study. Patients who withdraw should also be explicitly asked about the contribution of possible AEs to their decision to withdraw consent, and any AE information elicited should be documented.

Study Number: SLN360-002	Compound No.: SLN360
Protocol	Version: 1.0

The participant should withdraw consent preferably in writing and, if the participant refuses or is physically unavailable, the site should document and sign the reason for the participant's failure to withdraw consent in writing.

10.2.2. Participant Withdrawal from Study

Participants may withdraw from the study at any time and for any reason without the need for justification. Participants may also be withdrawn by the Investigator if, in the Investigator's opinion, further participation in the study would be deleterious to the participant's health. Reasons for withdrawal could include unacceptable adverse reactions, protocol violation or administrative reasons. To maintain the value and integrity of the study, excessive withdrawals should be avoided where possible.

Where consent remains, every effort must be made to follow-up participants and, other than re-dosing, the scheduled trial assessments should be performed if possible. A reason for withdrawal and an early withdrawal clinic assessments (consisting of assessments included in the Week 36 and EoS visit) as per the Time and Events tables ([Appendix 15.1](#) and [Appendix 15.2](#)) are essential.

10.2.3. Participant Withdrawal from Investigational Product

A participant will be withdrawn from treatment for any of the following reasons:

- Withdrawal of consent to continue with treatment. The reason for this will be documented if provided
- Lack of compliance, as assessed per the Investigator and/or the Sponsor
- Adverse events that cannot be tolerated by the participant

The reason(s) for withdrawal must be recorded in the eCRF. If a participant is withdrawn from treatment, every effort must be made for the participant to attend scheduled trial assessments if possible. Where a participant withdrawn from treatment is unable to attend scheduled assessments, every effort must be made to have them return for the Week 36 and EoS visits, if possible. Only if the participant is unable to attend scheduled assessments, follow-up may include contact with managing physicians or pharmacists, medical record review and limited phone call visits.

10.3. Long-term Follow-up

Where participants are lost to follow-up, continued efforts to locate participants during long-term follow-up until the EoS visit will be conducted in accordance with local regulations including available public records to determine vital status.

Study Number: SLN360-002	Compound No.: SLN360
Protocol	Version: 1.0

10.4. Treatment after the End of the Study

Participants will not be provided with study treatment following the end of the study. Regular treatment that participants received before entering the study can be continued following study completion.

10.5. Screening and Baseline Failures

If, after review pre-dose on Day -1 or Day 1, any eligibility criteria are found not to be met, the participant may be rescreened at the Investigator's discretion, or should be deemed a baseline failure. If a patient has a positive SARS-CoV-2 antigen lateral flow test or active coronavirus disease 2019 (COVID-19) infection during screening, rescreening should take place at least 4 weeks after the initial screening.

For participants who do not pass at screening or baseline, at least the ICF, demographics, inclusion and exclusion criteria, reason for screen failure and any AEs during screening will be collected in the eCRF. Information on screening and baseline failures will be collected and may be used for the final analysis.

10.6. Testing for SARS-CoV-2

Testing for SARS-CoV-2 will be completed using an antigen-based point-of-care lateral flow test at each visit. A positive test result should be confirmed with a second test immediately after the first.

In the event of a confirmed positive test result on or shortly before a dosing day, that dose administration should be delayed until the participant has a negative test result and dose administration is deemed clinically appropriate by the Investigator. If the first dose is delayed because of a positive test result, all subsequent visits should also be delayed accordingly. If a second or third dose is delayed because of a positive test result, the impacted visit will be delayed. All subsequent visits should be completed according to their original schedule as described in the Time and Events tables ([Appendix 15.1](#) and [Appendix 15.2](#)), i.e., not delayed.

Administration of doses outside the visit windows should not, *per se*, be grounds for withdrawing a participant unless this is deemed clinically appropriate by the Investigator.

A positive SARS-CoV-2 test result should be recorded as an AE, even if the participant is asymptomatic for COVID-19.

Study Number: SLN360-002	Compound No.: SLN360
Protocol	Version: 1.0

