Early safety, PK and pharmacology data from the SAD portion of the ongoing FIH study on SLN360 indicate that TEAEs were generally mild, and the most commonly reported TEAEs were low grade injection site events. Participants were administered a single dose of SLN360 up to 600 mg. Contrastingly, the maximum dose of SLN360 in the proposed study is lower (450 mg) and participants will receive study treatment with at least a 16-week gap between the two doses. Therefore, there are no expected risks to participants in terms of treatment doses or dose scheduling.

The promising early safety results from the ongoing FIH study of SLN360 suggest that the clinical benefits of SLN360 outweigh the anticipated risks. Subsequently, SLN360 could be a safe and effective treatment to lower Lp(a) and its associated cardiovascular risks in individuals with limited alternative treatment options.

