4. STUDY DESIGN

4.1. Summary of Study Design

4.1.1. Study Design

This is a multi-centre, randomised, double-blind, placebo-controlled Phase 2 study to investigate the efficacy, safety and tolerability of SLN360 in participants with elevated Lp(a) at high risk of ASCVD.

The study will be divided into three study periods, comprising screening, treatment and follow-up. An end-of-study (EoS) visit will be conducted to perform final safety and efficacy assessments.

Eligible participants will receive either placebo or SLN360 and will be randomised in the ratio 1:1:2:2:2 into five treatment groups:

- Group 1: Placebo administered subcutaneously at Weeks 0, 16 and 32 (dosing every 16 weeks [Q16W])
- Group 2: Placebo administered subcutaneously at Weeks 0 and 24 (dosing every 24 weeks [Q24W])
 - This group will be stratified so that half of participants are dosed to match the 300 mg Q24W SLN360 group and half are dosed to match the 450 mg Q24W SLN360 group) with respect to injected volume
- Group 3: SLN360 300 mg administered subcutaneously at Weeks 0, 16 and 32 (Q16W)
- Group 4: SLN360 300 mg administered subcutaneously at Weeks 0 and 24 (Q24W)
- Group 5: SLN360 450 mg administered subcutaneously at Weeks 0 and 24 (Q24W)

Placebo

The placebo has been chosen as the control treatment to assess whether any observed effects are treatment-related. The placebo is used since no appropriate active comparator is available; notably, there being no approved pharmacotherapy available that has been shown to yield a clinically meaningful lowering of Lp(a) in people with elevated levels.

Study Number: SLN360-002	Compound No.: SLN360
Protocol	Version: 1.0

Dose groups and treatment regimens are summarised in [Table 4](#).

[figure not shown]
Table 4 Dose groups and treatment regimens for the proposed Phase 2 study

Group	Regimen	No. of SLN360 doses	Total cumulative SLN360 administered
1	Placebo Q16W	-	-
2	Placebo Q24W	-	-
3	SLN360 300 mg Q16W	3	900 mg
4	SLN360 300 mg Q24W	2	600 mg
5	SLN360 450 mg Q24W	2	900 mg

Q16W=dosing every 16 weeks; Q24W=dosing every 24 weeks

An overview of the trial is presented in [Figure 2](#).

Figure 2 Overview of the Phase 2 study

Q16W=dosing every 16 weeks; Q24W=dosing every 24 weeks

Details of all dosing and assessment timepoints are outlined in the Time and Events tables ([Appendix 15.1](#) and [Appendix 15.2](#)).

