15. APPENDICES PROVIDED FOR STUDY SLN360-002

15.1. Appendix: Time and Events Table – Groups 1 and 3 (Dosing Every 16 Weeks)

Procedure	Optional Pre-screening	Screening	Intervention Period												Follow-up Period	EoS
			Week	-6	-4	0	1	4	8	12	16	20	24	28	32	36
Week	-6	-4	0	1	4	8	12	16	20	24	28	32	36	40	48	60
Day	-	-	1	8	29	57	85	113	141	169	197	225	252	281	337	421
Window (days)	-	-	-	-	±1	±2	±3	±4	±6	±7	±8	±9	±10	±12	±14	
Informed consent	X	X														
Eligibility assessment	X ^a	X														
Viral serology		X														
Demography		X														
Medical history		X														
Lifestyle and dietary restrictions		X	X									X				
Physical examination ^b		X	X	X	X	X	X	X	X	X	X	X	X	X	X	X
Concomitant/ prior medication		X	X	X	X	X	X	X	X	X	X	X	X	X	X	X
Randomisation		X														
Dose administration		X														
SARS-CoV-2 testing ^c	X	X	X	X	X	X	X	X	X	X	X	X	X	X	X	X

Study Number: SLN360-002
Protocol

Compound No.: SLN360
Version: Final Version

Study Number: SLN360-002		Compound No.: SLN360									
Protocol		Version: Final Version									

Procedure	Optional Pre-screening	Intervention Period										Follow-up Period	EoS				
		Week	-6	-4	0	1	4	8	12	16	20	24	28	32	36	40	48
Day	-	-	-	1	8	29	57	85	113	141	169	197	225	252	281	337	421
Window (days)	-	-	-	-	±1	±2	±3	±3	±4	±6	±7	±8	±9	±10	±12	±12	±14
Pregnancy testing ^d	X	X	X	X	X	X	X	X	X	X	X	X	X	X	X	X	X
Vital signs	X	X	X	X	X	X	X	X	X	X	X	X	X	X	X	X	X
Injection site reaction assessment																	
12-lead ECG ^e	X	X	X	X	X	X	X	X	X	X	X	X	X	X	X	X	X
Safety lab markers (blood) ^f	X	X	X	X	X	X	X	X	X	X	X	X	X	X	X	X	X
Urinalysis	X	X	X	X	X	X	X	X	X	X	X	X	X	X	X	X	X
PD markers ^g	X	X	X	X	X	X	X	X	X	X	X	X	X	X	X	X	X
Genotyping sample																	
Anti-drug antibody assessment sample		X	X														
AE recording		X	X	X	X	X	X	X	X	X	X	X	X	X	X	X	X

AE=adverse event; ECG=electrocardiogram; EoS=end-of-study; Lp(a)=lipoprotein(a); PD=pharmacodynamic; SARS-CoV-2=severe acute respiratory syndrome coronavirus 2

- Limited eligibility assessment to be conducted at the optional pre-screening visit
- A full physical examination is required at screening, pre-dose on Day 1 and EoS. An abbreviated physical examination is to be conducted at visits thereafter if indicated by symptoms, signs or other findings
- A SARS-CoV-2 antigen lateral flow test will be conducted pre-dose on each dosing day and at all other visits

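### Protocol 1.3 rests partly on a gap of at least 16 weeks between doses, but the visit windows and the 10.6 delay rule do not guarantee it in the three-dose Q16W groups, and no minimum interval is stated

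*Protocol*

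**What the plan says.** Protocol 1.3 (Potential Risks and Benefits) describes generally mild adverse events after single doses in Phase 1, notes that the maximum dose here is lower, and states that "participants will receive study treatment with at least a 16-week gap between the two doses". It then concludes that "there are no expected risks to participants in terms of treatment doses or dose scheduling".

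Protocol 4.1.1 gives Groups 1 (placebo) and 3 (SLN360 300 mg) three doses, at Weeks 0, 16 and 32. Groups 2, 4 and 5 receive two, at Weeks 0 and 24. Appendix 15.1 sets the Q16W target days and their visit windows.

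Protocol 10.6 covers a positive SARS-CoV-2 test around a dosing day. The dose waits for a negative test and for the Investigator's agreement that dosing is clinically appropriate. If the first dose is delayed, the whole calendar shifts. For later doses the rule differs: "If a second or third dose is delayed because of a positive test result, the impacted visit will be delayed", and then "All subsequent visits should be completed according to their original schedule". It adds that "Administration of doses outside the visit windows should not" in itself lead to withdrawal, unless the Investigator judges withdrawal clinically appropriate.

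**The concern.** The 16-week gap is one of the supports for the scheduling conclusion in 1.3. For it to hold as a minimum, something in the schedule must enforce it. The wording also assumes two doses, while the Q16W groups have three and therefore two gaps to protect.

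The 10.6 rule preserves spacing when dose 1 is late but shortens it when dose 2 is late. In the Q24W groups nothing follows dose 2, so no gap is lost. In the Q16W groups dose 3 follows, and it keeps its original date.

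At stake is a safety property that readers of the risk section, including ethics committees and investigators, would take as assured. The human data cited in 1.3 are single-dose, and the multiple-dose part of Phase 1 was still running (1.1.3). A shorter re-dosing interval is therefore one for which the protocol has model predictions but, as yet, no completed human repeat-dose data.

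**Working it through.** **Inputs.** Target days from Appendix 15.1: dose 1 on Day 1, dose 2 on Day 113 (Week 16), dose 3 on Day 225 (Week 32), Week 36 visit on Day 252. The extracted table is broken. The one copy of the 15.1 header whose Day and Window rows have equal length gives Day 113 ±4, Day 169 ±7 and Day 225 ±9. The Appendix 15.2 copies read one step narrower: ±3, ±6 and ±8. Both readings are carried through.

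**Stated figure.** 16 weeks = 112 days. Nominal gaps are 113 - 1 = 112 and 225 - 113 = 112 days. The statement is true on target days, with zero margin.

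**Windows alone.**
- Dose 1 to 2: (113 - 4) - 1 = 108 days (15.4 weeks). Narrower reading: (113 - 3) - 1 = 109 days.
- Dose 2 to 3: (225 - 9) - (113 + 4) = 99 days (14.1 weeks). Narrower reading: (225 - 8) - (113 + 3) = 101 days.
- Q24W: (169 - 7) - 1 = 161 days (23.0 weeks), or 162 on the narrower reading. The statement holds there.

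**Delay rule.** Dose 2 is given on Day 113 + d.
- Dose 3 on target: 225 - (113 + d) = 112 - d.
- Dose 3 at the early window edge: 216 - (113 + d) = 103 - d.
- Dose 3 at the late window edge: 234 - (113 + d) = 121 - d. This is at least 112 only if d is 9 or less.

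The protocol gives no delay lengths, so the values of d below are assumptions.

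| Delay d (days) | Dose 3 on Day 225 | Across the dose 3 window |
|---|---|---|
| 7 | 105 days (15.0 weeks) | 96 to 114 days |
| 14 | 98 days (14.0 weeks) | 89 to 107 days |
| 21 | 91 days (13.0 weeks) | 82 to 100 days |
| 28 | 84 days (12.0 weeks) | 75 to 93 days |

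**Comparison with the simulated intervals.** Protocol 8.2.1 lists Q3M as the shortest interval simulated, at both 300 mg and 450 mg, although the list is not presented as complete. Q3M is 84 days if a month was 28 days, and about 91 days if calendar months were used; the protocol does not say which. With dose 3 on target, the gap falls below 84 days when d exceeds 28, and below 91 days when d exceeds 21.

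**Search for a limit.** Protocol 8.1, 10.6 and Appendix 15.1, and the SAP, contain no maximum delay and no minimum interval. Section 8.1 refers to the IMP Handling Manual for further guidance; it was not available to check.

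**The case against.** The strongest reply is that 1.3 is background text describing nominal regimens, not a dosing rule. Any 16-week schedule with plus-or-minus windows can fall slightly short, and one word such as nominal would cure the sentence. That stands as far as the windows go. It does not cover the delay rule, which keeps dose 3 on its date however late dose 2 was.

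A second reply is that the safety substance is handled elsewhere. Section 8.2.1 simulates shorter intervals, predicts only modest liver-exposure increments and does not anticipate substantial accumulation. In rats, liver levels fell to 1% of peak or less by 3 weeks (1.1.2.2). Section 4.2 requires health and laboratory checks before dosing and obliges the Investigator to interrupt treatment when needed, and the IDMC reviews accruing data. This also stands, and it is why the point is minor. These safeguards are discretionary, however, and the human model fixes some parameters to values scaled from non-human primates because human liver data are lacking.

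Third, short gaps need long delays, and none is documented. That is fair. The only COVID-19 interval with a stated length concerns rescreening ("rescreening should take place at least 4 weeks after the initial screening"), and it does not govern delayed doses. Short delays can also be absorbed: up to 9 days can still leave 112 days if dose 3 is given late in its window.

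A reader might infer that Group 3 participants face a demonstrated hazard, or that gaps under 12 weeks are to be expected. The documents support neither. They show no harm at these intervals and give no frequency or length for delays. Nor is there a consequence for type I error or power.

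**Conclusion.** The point holds as a minor one. Section 1.3 claims a minimum gap that the Q16W schedule does not enforce. Windows alone allow 108 and 99 days (109 and 101 on the narrower reading) against 112 claimed. Section 10.6 can shorten the second gap by the full length of a dose 2 delay, with no cap in the protocol or SAP. The window result does not depend on how the broken table is read; the delay results rest on assumed delay lengths.

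The scope is narrow: Groups 1 and 3 only, and on active drug only the 40 planned participants in Group 3. Harm is unlikely down to the Q3M interval. Below it, protection depends on clinical judgement and not on a number. A rule in the IMP Handling Manual would close the operational gap but would not make the sentence in 1.3 match the protocol's own schedule.

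**What to change.** 1. Reword 1.3 to describe a nominal interval of 16 or 24 weeks between consecutive doses, subject to visit windows and a stated minimum.
2. Add to 10.6 a minimum interval between consecutive doses equal to the shortest interval simulated. The sponsor should confirm whether Q3M meant 84 or about 91 days. Either leaves in-window dosing unaffected, since that never falls below 99 days.
3. If the Week 32 dose would come too soon, move that dosing visit, with its pre-dose samples and its pre- and post-dose ECGs and vital signs, to the first permitted date, as 10.6 already does for a delayed dose. All other visits keep the original calendar, which protects the Week 36 endpoint.
4. Omit the dose if that date is on or after the Week 36 visit.

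The first permitted day is 113 + d + 84 = 197 + d, or 113 + d + 91 = 204 + d.

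| Minimum | Dose 3 can stay on Day 225 | Can stay in window (to Day 234) | Omitted (Day 252 or later) |
|---|---|---|---|
| 84 days | d up to 28 | d up to 37 | d of 55 or more |
| 91 days | d up to 21 | d up to 30 | d of 48 or more |

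A 112-day minimum would make the present sentence true but would cost more: a 14-day delay would push dose 3 to Day 239, outside its window.

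The cost is two text changes and, in rare cases, a rescheduled dosing visit. A participant with a long delay receives a later third dose, or 600 mg in total instead of 900 mg, which would also bear on the Week 48 and Week 60 secondary endpoints. The SAP need not change: 3.3.7 already lists all treatment data, and a summary of inter-dose intervals would be optional.

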11. ADVERSE EVENTS AND SERIOUS ADVERSE EVENTS

11.1. Definitions

11.1.1. Adverse Events

An AE is any untoward medical occurrence associated with the use of a drug/investigational drug in humans, whether or not considered drug related. An AE can therefore be any unfavourable and unintended sign, symptom or disease that either emerges during the study or, if present at screening, worsens during the study, regardless of the suspected cause of the event.

11.1.2. Adverse Events of Special Interest

An AE of special interest, whether serious or non-serious, is one of scientific and medical concern specific to the Sponsor's study drug/device or programme, which warrants ongoing monitoring and rapid communication by the Investigator to the Sponsor. Such an event might warrant further investigation to characterise and understand it. Adverse events of special interest may include events noted in prior studies. No AEs have been determined, for reporting purposes, to be AEs of special interest in this study.

11.1.3. Serious Adverse Events

An SAE is any untoward medical occurrence that, at any dose:

1. Results in death
2. Is life-threatening

NB: An AE is 'life-threatening' if the patient is at immediate risk of death from the event as it occurs (i.e., does not include a reaction that might have caused death if it had occurred in a more serious form). For instance, drug-induced hepatitis that resolves without evidence of hepatic failure would not be considered life-threatening, even though drug-induced hepatitis can be fatal.

3. Requires in-patient hospitalisation or prolongation of existing hospitalisation (see below)
4. Results in persistent or significant disability/incapacity (disability is defined as a substantial disruption of a person's ability to conduct normal life functions)
5. Results in a congenital anomaly/birth defect
6. Results in an important medical event

NB: Important medical events that may not result in death, be life-threatening, or require hospitalisation may be considered SAEs when, based upon appropriate medical

Study Number: SLN360-002	Compound No.: SLN360
Protocol	Version: 1.0

judgement, they may jeopardise the patient and may require medical or surgical intervention to prevent one of the outcomes listed in this definition. Examples of such events are invasive or malignant cancers, intensive treatment in an emergency department or at home for allergic bronchospasm, blood dyscrasias or convulsions that do not result in hospitalisation.

Hospitalisation

Adverse events requiring hospitalisation or prolongation of hospitalisation should be considered serious. In the absence of an AE, the participating Investigator should not report hospitalisation or prolongation of hospitalisation. In general, hospitalisation signifies that the participant has been detained (usually involving at least an overnight stay) at the hospital or emergency ward for observation and/or intervention that would not have been appropriate in the treating physician's office or outpatient setting. Complications that occur during hospitalisation are AEs. If a complication prolongs hospitalisation or fulfils any other seriousness criteria, the event is serious. When in doubt as to whether hospitalisation occurred or was necessary, the AE should be considered serious.

In the following situations, hospitalisation would not qualify as serious:

- Hospitalisation or prolongation of hospitalisation is needed for a procedure required by the protocol
- Hospitalisation or prolongation of hospitalisation is part of a routine procedure followed by the study centre. This should be recorded in the study file
- Hospitalisation for survey visits or annual physicals fall into the same category
- Hospitalisation is required for an elective intervention of a pre-existing condition that has not worsened from study treatment
- Hospitalisation for social reasons/circumstances

11.1.4. Adverse Drug Reactions

All noxious and unintended responses to an IMP (i.e., where a causal relationship between an IMP and an AE is at least a reasonable possibility) related to any dose should be considered adverse drug reactions.

Suspected unexpected serious adverse reactions (SUSARs) are SAEs, classed as related, which are not specified as expected in the approved IB. An unexpected adverse drug reaction is defined as an adverse reaction, the nature and severity of which is not consistent with the applicable product information (e.g., the IB for an unapproved IMP).

Study Number: SLN360-002	Compound No.: SLN360
Protocol	Version: 1.0

